
Conditions to be fulfilled for asciminib switch
	
1. Failure to bosutinib treatment up to 96 weeks after the last patient received the first dose (adapted from the 2013 ELN Guidelines; Baccarani et al 2013). Patients must meet at least 1 of the following criteria. Failure is defined as follows:
 
 • Three months after the initiation of therapy or thereafter: No CHR or > 95% Ph+ metaphases. • Six months after the initiation of therapy or thereafter: BCR-ABL1 ratio > 10% IS and/or > 65% Ph+ metaphases. • Twelve months after initiation of therapy or thereafter: BCR-ABL1 ratio > 10% IS and/or > 35% Ph+ metaphases. • At any time after the initiation of therapy, loss of CHR, CCyR or PCyR. • At any time after the initiation of therapy, detection of new BCR-ABL1 mutations which potentially cause resistance to study treatment (asciminib or bosutinib). • At any time after the initiation of therapy, confirmed loss of MMR in 2 consecutive tests. • At any time after the initiation of therapy, new clonal chromosome abnormalities in Ph+ cells: CCA/Ph+. 
Conditions preventing patients to switch to asciminib:
 
 • Any Grade 3 or 4 toxicity which has not resolved to Grade 2 or lower within 28 days and before starting asciminib treatment. • Asymptomatic (Grade 2) pancreatitis if not resolved within 28 days • Disease progression while on bosutinib treatment. The following events are considered disease progression: 
 • Accelerated phase (AP) as defined by any of the following: 
 • ≥ 15% blasts in the peripheral blood or bone marrow aspirate, but < 30% blasts in both the peripheral blood and bone marrow aspirate. • ≥ 30% blasts plus promyelocytes in peripheral blood or bone marrow aspirate. • ≥ 20% basophils in the peripheral blood. • Thrombocytopenia (< 100 x 10⁹/L) that is unrelated to therapy. • Blast crisis (BC) as defined by any of the following: 
 • ≥ 30% blasts in peripheral blood or bone marrow aspirate

	
 • Appearance of extramedullary involvement other than hepatosplenomegaly proven by biopsy (i.e., chloroma). • QTcF at time of switch > 480 msec or inability to determine QTc interval
Investigational and reference therapy	Asciminib 40 mg BID Bosutinib 500 mg QD

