The frequency of bone marrow aspirate (BMA) to perform cytogenetic analysis has been decreased in accordance with treatment guidelines (European Leukemia Network (ELN) Guidelines ([Baccarani et al 2013](#)), [National Comprehensive Cancer Network \(NCCN\)](#) (Clinical Practice Guidelines in Oncology-Chronic Myeloid Leukemia v4.2018)). Initially BMAs were foreseen at screening, every 24 weeks thereafter and at end of treatment. With the protocol amendment BMA is no longer needed for patients that have achieved MMR during study, however BMA assessment is requested at the time of end of treatment for biomarker analysis.

Toxicity studies performed in rats, dogs and cynomolgus monkeys identified the pancreas as potential target tissues. Therefore the assessment for laboratory parameters that are associated with pancreatitis were part of the inclusion criteria (amylase, lipase). Serum lipase is the preferred test due to its improved sensitivity, and a threshold concentration of 2-3 x ULN is recommended for the diagnosis of pancreatitis. There are a number of other conditions that can elevate lipase, including TKI pretreatment, thus the screening threshold for lipase is increased from \leq ULN to $\leq 1.5 \times$ ULN (CTCAE v4.03 grade 1), as patients with history of acute pancreatitis within 1 year of study and history of chronic pancreatitis are excluded. Amylase is not a specific marker for pancreatitis, as up to 60% of total serum amylase originates from non-pancreatic sources. Its short half-life reduces its value as a diagnostic test in the early clinical course. Lipase has replaced amylase as the biochemical test of choice for acute pancreatitis due to its higher specificity ([Basnayake 2015](#)), therefore the requirement of amylase \leq ULN at screening has been removed.

Assessments for visits at weeks 6, 10 and 14 will be limited to the monitoring of the bone marrow function to allow for adjustments of study treatment. Assessments will comprise a complete blood count to detect neutropenia and thrombocytopenia which are among the most frequent adverse reactions [[Asciminib Investigator's Brochure](#), [Bosutinib label](#)]. The physical examination must be done at site only in case of previous or newly occurring adverse events.

[figure not shown]
The concomitant medication section has been updated to reflect the most recent clinical updates on asciminib as well to align with the Bosutinib label.

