 - Hematologic intolerance: Patients with grade 3 or 4 toxicity (absolute neutrophil count [ANC] or platelets) while on therapy that is recurrent after dose reduction to the lowest doses recommended by manufacturer
6. Eastern Cooperative Oncology Group (ECOG) performance status (PS) of 0, 1, or 2
7. Adequate end organ function as defined by (as per central laboratory tests):
 - Total bilirubin $\leq 1.5 \times$ ULN except for patients with Gilbert's syndrome who may only be included if total bilirubin $\leq 3.0 \times$ ULN or direct bilirubin $\leq 1.5 \times$ ULN

- Aspartate transaminase (AST) $\leq 3.0 \times \text{ULN}$
 - Alanine transaminase (ALT) $\leq 3.0 \times \text{ULN}$
 - Serum lipase $\leq 1.5 \times \text{ULN}$. For serum lipase $> \text{ULN} - \leq 1.5 \times \text{ULN}$, value must be considered not clinically significant and not associated with risk factors for acute pancreatitis
 - Alkaline phosphatase $\leq 2.5 \times \text{ULN}$
 - Creatinine clearance $\geq 50 \text{ mL/min}$ as calculated using Cockcroft-Gault formula
8. Patients must avoid consumption of grapefruit, Seville oranges or products containing the juice of each during the entire study and preferably 7 days before the first dose of study medications, due to potential CYP3A4 interaction with the study medications. Orange juice is allowed.
9. Written informed consent obtained prior to any screening procedures.
- 10a. Patients must have the following electrolyte values (as per central laboratory tests) within normal limits or corrected to be within normal limits with supplements prior to first dose of study medication:
- Potassium (potassium increase of up to 6.0 mmol/L is acceptable at study entry if associated with creatinine clearance within normal limits)
 - Total calcium (corrected for serum albumin); (calcium increase of up to 12.5 mg/dl or 3.1 mmol/L is acceptable at study entry if associated with creatinine clearance within normal limits)
 - Magnesium, with the exception of magnesium increase $> \text{ULN} - 3.0 \text{ mg/dL}$; $> \text{ULN} - 1.23 \text{ mmol/L}$ associated with creatinine clearance (calculated using Cockcroft-Gault formula) within normal limits.
11. Evidence of typical BCR-ABL1 transcript [e14a2 and/or e13a2] at the time of screening which are amenable to standardized RQ-PCR quantification.

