5.3 Exclusion criteria

Patients eligible for this study must not meet **any** of the following criteria:

1. Known presence of the T315I or V299L mutation at any time prior to study entry
2. Known second chronic phase of CML after previous progression to AP/BC
3. Previous treatment with a hematopoietic stem-cell transplantation
4. Patient planning to undergo allogeneic hematopoietic stem cell transplantation
5. Cardiac or cardiac repolarization abnormality, including any of the following:
 - History within 6 months prior to starting study treatment of myocardial infarction (MI), angina pectoris, coronary artery bypass graft (CABG)
 - Clinically significant cardiac arrhythmias (e.g., ventricular tachycardia), complete left bundle branch block, high-grade AV block (e.g., bifascicular block, Mobitz type II and third degree AV block)
 - QTcF at screening $\geq 450 \text{ msec}$ (male patients), $\geq 460 \text{ msec}$ (female patients)
 - Long QT syndrome, family history of idiopathic sudden death or congenital long QT syndrome, or any of the following:

- Risk factors for Torsades de Pointes (TdP) including uncorrected hypokalemia or hypomagnesemia, history of cardiac failure, or history of clinically significant/symptomatic bradycardia
 - Concomitant medication(s) with a “Known risk of Torsades de Pointes” per www.crediblemeds.org/ that cannot be discontinued or replaced 7 days prior to starting study drug by safe alternative medication.
 - Inability to determine the QTcF interval
6. Severe and/or uncontrolled concurrent medical disease that in the opinion of the investigator could cause unacceptable safety risks or compromise compliance with the protocol (e.g. uncontrolled diabetes, active or uncontrolled infection, pulmonary hypertension)
 7. History of acute pancreatitis within 1 year of study entry or past medical history of chronic pancreatitis
 9. History of acute or chronic liver disease
 10. Known presence of significant congenital or acquired bleeding disorder unrelated to cancer
 11. History of other active malignancy within 3 years prior to study entry with the exception of previous or concomitant basal cell skin cancer and previous carcinoma in situ treated curatively
 12. Known history of Human Immunodeficiency Virus (HIV), chronic Hepatitis B (HBV), or chronic Hepatitis C (HCV) infection. Testing for Hepatitis B surface antigen (HBs Ag) and Hepatitis B core antibody (HBcAb / anti HBc) will be performed at screening

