Grade 1 (> ULN - 1.5 x ULN)	Recommendation: Maintain dose level, measure 2x week	Recommendation: Maintain dose level, measure 2x week
Grade 2 (> 1.5 - 2.0 x ULN)	Recommendation: Maintain dose level, measure 2x week	Recommendation: Maintain dose level, measure 2x week
Grade 3 (> 2.0 - 5.0 x ULN)	Mandatory: Hold dose until resolved to Grade ≤ 1 or baseline, then: If resolved in ≤ 7 days, then reduce dose ↓ 1 dose level If resolved in > 7 days, then discontinue treatment and obtain appropriate imaging (i.e., MRI, CT scan or ultrasound).	Mandatory: Hold dose until resolved to Grade ≤ 1 or baseline, then: If resolved in ≤ 7 days, then reduce dose ↓ 1 dose level If resolved in > 7 days, then discontinue treatment and obtain appropriate imaging (i.e., MRI, CT scan or ultrasound).
Grade 4 (> 5.0 x ULN)	Mandatory: Permanently discontinue patient from study drug treatment. Obtain appropriate imaging (i.e., MRI, CT scan or ultrasound).	Mandatory: Permanently discontinue patient from study drug treatment. Obtain appropriate imaging (i.e., MRI, CT scan or ultrasound).

Dose modifications for both asciminib and bosutinib		
Please note that if a patient requires a dose interruption of > 28 days for each toxicity, then the patient must be discontinued from the study treatment		
Worst toxicity CTCAE Grade 4.03	Asciminib	Bosutinib
Vascular disorders		
Hypertension		
CTCAE Grade 3	Mandatory: Hold dose until resolved \leq Grade 1, then reduce dose \downarrow 1 dose level	Mandatory: Hold dose until resolved \leq Grade 1, then reduce dose \downarrow 1 dose level
CTCAE Grade 4	Mandatory: Permanently discontinue patient from study drug treatment.	Mandatory: Permanently discontinue patient from study drug treatment.
Gastro intestinal		
Pancreatitis		

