Grade 2 (radiologic findings for pancreatitis as per CTCAE v4.03, for increased enzymes please see table for asymptomatic amylase and/or lipase elevation)	Mandatory: If asymptomatic radiologic pancreatitis, hold treatment until recovery of the radiologic findings. If treatment delay is \leq 21 days, then reduce dose \downarrow 1 dose level. If treatment delay > 21 days, discontinue treatment and keep monitoring with appropriate imaging (i.e., MRI, CT scan or ultrasound).	Mandatory: If asymptomatic radiologic pancreatitis, hold treatment until recovery of the radiologic findings. If treatment delay is \leq 21 days, then reduce dose \downarrow 1 dose level. If treatment delay > 21 days, discontinue treatment and keep monitoring with appropriate imaging (i.e., MRI, CT scan or ultrasound).
Grade \geq 3	Mandatory: Permanently discontinue patient from study drug treatment. Obtain appropriate imaging (i.e., MRI, CT scan or ultrasound).	Mandatory: Permanently discontinue patient from study drug treatment. Obtain appropriate imaging (i.e., MRI, CT scan or ultrasound).
Diarrhea***		
Grade 1	Recommendation: Maintain dose level but, initiate anti-diarrhea treatment	Recommendation: Maintain dose level but, initiate anti-diarrhea treatment
Grade 2	Recommendation: Hold dose until resolved to \leq grade 1, then maintain dose level. If diarrhea returns as \geq grade 2, then hold dose until resolved to \leq grade 1, then reduce dose \downarrow 1 dose level	Recommendation: Hold dose until resolved to \leq grade 1, then maintain dose level. If diarrhea returns as \geq grade 2, then hold dose until resolved to \leq grade 1, then reduce dose \downarrow 1 dose level
Grade 3	Recommendation: Hold dose and discontinue patient from study drug treatment	Mandatory: Hold dose until recovery to \leq grade 1. Recommendation: Bosutinib may then be resumed at \downarrow 1 dose level
Grade 4	Mandatory: Permanently discontinue patient from study drug treatment	Mandatory: Hold dose until recovery to \leq grade 1. Recommendation: Bosutinib may then be resumed at \downarrow 1 dose level

Dose modifications for both asciminib and bosutinib		
Please note that if a patient requires a dose interruption of > 28 days for each toxicity, then the patient must be discontinued from the study treatment		
Worst toxicity CTCAE Grade 4.03	Asciminib	Bosutinib
Skin and subcutaneous tissue disorders		
Rash/photosensitivity		

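### The summary's conditions for switching from bosutinib to asciminib set looser lipase and pancreatitis limits than trial entry, without giving a reason (minor)

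*Combined protocol and SAP*

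**What the plan says.** **Switch (Amendment 3, Protocol summary, conditions for asciminib switch).** Three safety conditions prevent a switch, besides disease progression:
- The general toxicity condition is "Any Grade 3 or 4 toxicity which has not resolved to Grade 2 or lower within 28 days and before starting asciminib treatment".
- The only condition that names the pancreas is "Asymptomatic (Grade 2) pancreatitis if not resolved within 28 days".
- The cardiac condition is "QTcF at time of switch > 480 msec or inability to determine QTc interval".

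No lipase limit, pancreatitis-history exclusion or reduced starting dose is listed.

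**Entry (Sections 5.2 and 5.3).** Inclusion criterion 7 caps serum lipase at 1.5 x ULN. For results between ULN and 1.5 x ULN, the "value must be considered not clinically significant and not associated with risk factors for acute pancreatitis". Exclusion criterion 7 reads "History of acute pancreatitis within 1 year of study entry or past medical history of chronic pancreatitis". The Amendment 2 rationale links the two: the lipase limit could be raised from ULN to 1.5 x ULN "as patients with history of acute pancreatitis within 1 year of study and history of chronic pancreatitis are excluded".

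**On treatment (Table 6-2, both drug columns).** The lipase band "Grade 2 (> 1.5 - 2.0 x ULN") carries a recommendation to keep the dose and measure twice weekly. Grade 3 lipase means holding the drug until Grade 1 or lower, or baseline. The drug then resumes one dose level lower if this took 7 days or less, and is otherwise discontinued. For Grade 3 or worse pancreatitis the instruction is "Permanently discontinue patient from study drug treatment. Obtain appropriate imaging".

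**The concern.** A switching patient is starting asciminib for the first time, so the natural benchmarks are the entry limits and the rules for resuming a drug after a pancreatic event. As summarised, the switch conditions fall short of both. The entry limits for lipase and pancreatitis history were justified together in Amendment 2, and the switch list carries neither. The Amendment 3 rationale for the switch gives no reason for a looser pancreatic standard.

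The issue is patient safety. Section 1.2.1.1 names the pancreas as a potential target tissue. Section 2.3 reports phase I pancreatitis in two patients escalated from 40 to 80 mg and in one at 150 mg BID; it describes none at 40 mg BID. Section 1.2.1.2 gives increased lipase as the most common Grade 3/4 event, at 17.1%. These figures describe asciminib's own risk. They do not say how many bosutinib failures would have raised lipase when they switch.

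A lesser issue is interpretation. The safety of asciminib after bosutinib failure is a secondary objective (Table 3-1). A pancreatic abnormality already present at the first dose makes later pancreatic events harder to attribute.

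**Working it through.** No power or sample-size figure is involved. The check sets the rules side by side, using the protocol's own grade bands.

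**1. Lipase ceiling at the first asciminib dose**
- Entry: 1.5 x ULN (Section 5.2, criterion 7).
- Switch: Grade 2 or lower is enough, and Table 6-2 puts the top of Grade 2 at 2.0 x ULN.
- Difference: 2.0 - 1.5 = 0.5 x ULN. Ratio: 2.0 / 1.5 = 1.33, so the switch ceiling is one third higher.

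A patient with lipase above 1.5 and up to 2.0 x ULN fails entry but is not barred from switching.

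**2. Comparison of rules**

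| Situation | Entry | Table 6-2, either drug | Switch list |
|---|---|---|---|
| Lipase above 1.5 to 2.0 x ULN | Not eligible | Keep dose, measure twice weekly | Not barred |
| After Grade 3 lipase | At most 1.5 x ULN | Resume only at Grade 1 or lower, or baseline, one dose level down; stop if this takes more than 7 days | Not barred once Grade 2 or lower within 28 days |
| Grade 3 or worse pancreatitis, settled | Acute pancreatitis within 1 year excluded | Permanent stop | Not expressly barred |

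**3. QTcF as a contrast.** The switch limit is also looser than entry here: 480 msec, against 450 (men) and 460 (women). However, Section 6.3.2 uses 480 msec as the level at which re-introduction may be considered, so that relaxation matches a restart rule. After a Grade 3 rise, Grade 2 lipase matches neither the entry limit nor the restart rule.

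**4. Which group the 17.1% describes.** In Section 1.2.1.2 the figure follows the list of events at 40 mg BID (n = 35), in a paragraph that opens with all 150 monotherapy patients.
- 6 / 35 = 17.1%
- 25 / 150 = 16.7% and 26 / 150 = 17.3%

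No count out of 150 gives 17.1%. The figure therefore appears to be 6 of 35 patients at the dose switchers would receive. This is an inference; the text does not state the count.

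**5. How many patients could be concerned.** Planned bosutinib arm: 222 x 1/3 = 74. The Amendment 3 rationale counted 4 possible switchers by 15-Oct-2018. A patient must also have a pancreatic abnormality at about the time of documented failure. The documents give no rate for that, so no event count is derived.

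**The case against.** **The operative section is missing.** Section 7.1.2.2 holds the detailed switch criteria, and the supplied text ends before it. It may contain a lipase limit. This stands: the point applies to the summary, and to that section only if it reads the same.

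**Grade 2 lipase has an anchor in the protocol.** A reader might infer that the switch level matches nothing else in the plan. That goes too far, because Table 6-2 keeps patients on full-dose asciminib at new Grade 2 lipase. But that rule concerns continuing a drug already being taken. For resuming after Grade 3, the same table demands more. A footnote also stops treatment permanently if asymptomatic Grade 2 elevations recur at the reduced dose.

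**Severe pancreatitis may already be covered.** A reader might infer that the protocol positively permits asciminib after Grade 3 or worse pancreatitis. The documents do not support that. The stop in Table 6-2 is worded for study drug, the table covers both drugs, and the glossary defines study treatment as drugs in any arm. It may be meant to bar asciminib too. Equally, every switcher has already stopped bosutinib, and the switch list does not settle the matter.

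**Few patients can qualify.** Section 4.1.1 requires failure documented while on bosutinib. Grade 3 or worse pancreatitis and Grade 4 lipase end bosutinib, so the event and the failure must nearly coincide. This stands and limits the size of the problem.

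**A looser bar may be deliberate.** Switchers have failed at least a third TKI, and Section 2.2 requires investigator discretion and patient interest. That is a fair reason for some relaxation, but it is not given for the pancreatic limits. Entry is also investigator-led and still has numerical limits.

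**Conclusion.** The concern holds in a narrow form, as a minor point. As summarised, asciminib may be started after bosutinib failure with lipase one third above the entry cap, including just after a Grade 3 rise, and with no express bar after settled Grade 3 or worse pancreatitis. No reason is given for this looser starting standard.

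Two stronger conclusions are not supported. A reader might infer that the protocol contradicts itself; it does not, because entry, on-treatment and switch rules govern different decisions. A reader might also infer that efficacy conclusions are affected. They are not: the Amendment 3 rationale counts patients who meet the failure criteria as non-responders from then on and analyses post-switch efficacy separately.

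The verdict rests on the summary being representative of Section 7.1.2.2, and on the Grade 3/4 bullet being the only one that reaches lipase. The number affected is unknown and may be zero.

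**What to change.** In the summary, and in Section 7.1.2.2 if it reads the same:

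1. Require lipase at or below 1.5 x ULN before the first asciminib dose, as at entry.
2. State that Grade 3 or worse pancreatitis on bosutinib bars the switch, so that the intended reach of Table 6-2 is explicit.

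As an optional clarification only, the Grade 2 pancreatitis bullet could say, like the bullet above it, that resolution must come before the first asciminib dose; its natural reading already implies this.

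The 28-day window and the general Grade 2 recovery rule can stay. The full one-year look-back need not be copied, because Table 6-2 itself allows dosing to resume, one level down, after Grade 2 pancreatitis with a delay of 21 days or less. A Grade 4 lipase rise without pancreatitis that has returned to 1.5 x ULN or below need not bar the switch. If the looser limits are intended, a sentence of justification would serve instead.

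The cost is a few words and apparently no new test. Table 7-2 already schedules chemistry at switch screening if not done at end of treatment. Lipase is in the chemistry panel of the Amendment 1 text (Section 7.2.2.5.2); the Amendment 3 panel is not supplied. The real downside is that a few bosutinib failures with limited options would switch later or not at all.

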1.1 Overview of disease pathogenesis, epidemiology and current treatment

Chronic myeloid leukemia (CML) is a hematological stem cell disorder characterized by a specific chromosomal translocation leading to the Philadelphia (Ph) chromosome which is detected in 95% of patients (Nowell and Hungerford 1960; Rowley 1973). The molecular consequence of the translocation is the fusion of the *ABL1* proto-oncogene to the *BCR* gene resulting in the production of an activated form of the ABL1 protein tyrosine kinase (TK) (Bartram et al 1983; Heisterkamp et al 1983). BCR-ABL1 drives the growth factor independence, increased proliferation, genomic instability, suppression of apoptosis and alteration of the adhesive properties of CML cells (Hochhaus 2009) and the expression of BCR-ABL1 in mice results in the development of a CML-like disease (Daley et al 1990; Kelliher et al 1990). This evidence that BCR-ABL1 is a genetic driver of CML was subsequently confirmed by the clinical efficacy of imatinib in patients [IRIS Study STI571A0106].

Clinically, CML is characterized by overproduction of immature myeloid cells and mature granulocytes in the spleen, bone marrow and peripheral blood. Most patients, however, present in the CP, characterized by splenomegaly and leukocytosis with generally few symptoms. CML progresses through three distinct phases of increasing refractoriness to therapy: chronic phase (CP), accelerated phase (AP), and blast crisis (BC). With conventional chemotherapy, such as busulfan or hydroxyurea, the median survival time commonly reported for CML was about 4 years, but progression to AP and BP was only slightly delayed. Interferon-alfa delayed progression significantly, with a median survival of approximately 6 years. However, during the last decade, TK inhibitor (TKI) therapy became the standard treatment for most patients with CML, with complete cytogenetic response rates of 70% to 90% and 5-year progression-free survival and overall survival of 80% to 95% commonly reported (Vardiman 2009).

The National Comprehensive Cancer Network (NCCN) guideline on CML (NCCN guideline v 1.2014) and the European Leukemia Net (ELN) (Baccarani et al 2013) recommend continuing TKI treatment indefinitely in all responding patients. The first TKI, imatinib mesylate (imatinib, STI571, Gleevec™/Glivec™), an adenosine triphosphate (ATP)-competitive TKI with selectivity towards BCR-ABL1, revolutionized treatment of CML and significantly improved the prognosis of patients since its approval in 2001. It is effective in most patients with CML at well-tolerated doses, and is indicated as frontline therapy for Ph+ CML-CP and in patients with Ph+ CML in blast crisis (BC), accelerated phase (AP), or in CP after failure of interferon-alpha therapy. However, despite the remarkable efficacy of imatinib, some patients are either intolerant to the drug or can develop resistance (O'Hare 2006). Imatinib resistance is primarily due to nucleotide substitutions in BCR-ABL1, which encode mutant forms of protein's tyrosine kinase domain that impair imatinib binding. Over-expression of the BCR-ABL1 protein may also cause resistance. Rates of resistance increase with each stage of progression of CML (CP < AP < BC) (Branford 2003).

Multiple agents, including nilotinib, dasatinib, ponatinib, bosutinib, radotinib (Korea) and omacetaxine (USA, Canada) are able to combat various forms of imatinib-resistant CML and are currently approved for patients with CML-CP previously treated with prior therapy. With the exception of omacetaxine, which is a cytotoxic chemotherapeutic agent, all of these drugs

are ATP-competitive TKIs. Like imatinib, nilotinib, dasatinib and most recently bosutinib are also indicated for the treatment of patients with newly diagnosed CML. The activity of nilotinib or dasatinib in patients previously treated with a second generation TKI is not known. In contrast to the ATP-competitive TKIs, asciminib inhibits the enzymatic activity of BCR-ABL1 through an allosteric mechanism.

There remains an unmet need for new compounds in patients with CML who have failed at least two prior TKIs. Current practice suggests that a second generation TKI will have been used for first line therapy for about one half of patients with CML, meaning that most patients who have failed at least two prior TKIs will have failed at least one if not two second generation TKIs: dasatinib and/or nilotinib. Potentially, such patients may also have failed bosutinib and/or ponatinib (Soverini 2014). Patients having failed at least two TKIs may have limited sensitivity to the remaining available agents and, thus, there exists a need for new safe and effective therapy. In addition, mutations will have developed in 21 to 33% of patients that prevent the use of specific TKIs, increasing the need for a better and alternative compound (Soverini 2014). Omacetaxine, a chemotherapeutic agent, is available for patients who have failed at least two prior TKIs under these conditions but only in the US and Canada. This agent is not available for most patients globally, where a bigger unmet medical need is present. Thus, there remains an unmet need for active and safe drugs in patients with CML who have failed at least two prior tyrosine kinase inhibitors (TKI), even in the presence of approved drugs, as described below.

